6.4 Analysis of Secondary Outcomes

The secondary outcomes included mean changes in the levels of lifetime risk of ASCVD based on the China-PAR model, SBP, DBP, FBG, and non-HDL-C, as well as changes in the proportions of obesity, daily smoking, and insufficient physical activity, from baseline to the 12 months. The assessment of secondary outcomes of continuous variables will be analysed using linear mixed effects models, same as the analysis method of primary outcome, and the categorical variables will be analysed using the generalised linear mixed effects models. Villages will be adjusted in the

models as a random effect. The net differences between the two groups were assessed by the models, with multivariable adjustment by baseline covariates including age, sex, education, occupation, annual household income, marital status, and social medical insurance.

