5. DATA MANAGEMENT

5.1 Data Collection

The participants basic information, including demographic information, socioeconomic status (SES), and medical history will be collected at baseline survey. And information of study outcomes (for participants in both intervention and control groups) will be collected at baseline and each follow-up visits at 3th month, 6th month, 9th month, and 12th month.

These data will be collected in three ways:

(1) standardized electronic questionnaire interview (basic information, lifestyle behaviours, and medication use);

(2) physical examination (blood pressure, height, weight, waist circumference, grip strength, walking speed, and vital capacity);

(3) fingertip blood sample collection (fast test for blood glucose and lipid).

Regarding assessment of the metabolic risk factors, to be more specific, blood pressure will be measured twice on the right upper arm using a standard sphygmomanometer (Omron HEM-7121, Omron Corporation, Japan) after 5 minutes of rest in the sitting position. Blood glucose and blood lipid will be tested by the rapid blood glucose analyser (BeneCheck BK6-20 M Multi-Monitoring System, Suzhou Pu Chun Tang Biotechnology, China) and the fast photochemical lipid analyser (CardioChek PA Analyzer; Polymer Technology Systems, USA), respectively. Body mass index (BMI) will be calculated as body weight in kilograms divided by the squared value of height in meters, with obesity is defined as a BMI≥28.0 kg/m².

For assessment of lifestyle behaviours, smoking status (never, former, or current smokers) and frequency will be inquired in the questionnaire. Daily smoking is defined as self-reported consuming tobacco products every day. Regarding physical activity, we will ask the participants about the time they spend on four types of

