

TABLES

Table 2. Cardiovascular	risk factors to	be assessed in t	the SMARTER study
	11511 100001 5 00		

Risk factors	Indicators	Warning criteria
10-year risk of ASCVD	Risk (value)	≥10%
	Risk (stratification)	High-risk
1. Hypertension	SBP	≥130 mmHg
	DBP	≥80 mmHg
2. Diabetes	FBG	≥6.1 mmol/L
3. Dyslipidaemia	TC	\geq 5.2 mmol/L
	Non-HDL-C	\geq 3.4 mmol/L
4. Obesity	BMI	Overweight: $\geq 24 \text{ kg/m}^2$, Obesity: $\geq 28 \text{ kg/m}^2$
	Bodyweight	According to the BMI criteria
	Waist circumstance	Males: ≥90 cm, Females: ≥85 cm
5. Smoking	Daily smoking amount	>0
	Heaviness of Smoking Index (HSI)	Heavy dependence
6. Alcohol use	Daily consumption of pure alcohol	≥15g (on average)
7. Physical activity	Total physical activity	<3000 MET-min/wk
	Exercise intensity	No exercise
	Weekly exercise time	Moderate-intensity aerobic activities<150 minutes, or vigorous-intensity aerobic activities<75 minutes
8. Unhealthy diet	Fruit	Less than everyday
	Fresh vegetables	Less than everyday
	Whole grains	Less than everyday
	Bean and bean food	Less than four days per week
	Red meat	Everyday
9. Sleep deprivation	Sleep duration	<6 hours/day (on average)
10. Medication adherence	Self-reported adherence	Intermittent or absent use of medications

Risk factors	Targets	Principles
Hypertension	SBP/DBP	Age<80: <130/80 mmHg; Age≥80: <150/90 mmHg (recommended; allow for adjustment according to the circumstances)
Diabetes	FBG	Participants without a diagnosis of DM: <6.1 mmol/L; DM patients: <7.0 mmol/L
Dyslipidaemia	Non-HDL-C	Age<75, no diagnosis of DM: <3.4 mmol/L; Age<75, DM patients: <2.6 mmol/L; Age ≥75: lipid lowering target should be set under guidance of the physicians in higher-level hospitals

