Obesity	Weight loss	BMI<28 kg/m ² : with a body weight at BMI 24 as the target weight, setting the weight loss goal to be achieved in four stages during follow-up; BMI≥28 kg/m ² : setting a 15% of the current body weight as the bodyweight loss goal to be achieved in four stages during follow-up
Smoking	Smoking cessation	Never smokers: no smoking; Current smokers: quitting smoking
Alcohol use	Alcohol reduction	Never drinkers or non-weekly drinkers: no alcohol; Weekly drinkers: limiting the frequency and consumption of alcohol (pure alcohol should not exceed 15g per day on average)
Physical activity	Daily step count; Exercise frequency	Age<60: the daily step count should reach 8000- 10000 per exercise day; Age≥60: the daily step count should reach 6000- 8000 per exercise day; At the first 6 months of the study, it is recommended to exercise at least 3 days per week; at the last 6 months, competent participants are recommended to exercise 5 days per week

Table 3. Principles for Establishing Individualized Health Promotion Goals

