3.5.2 Secondary Outcomes

(1) Mean changes in lifetime risk of ASCVD based on the China-PAR risk prediction model from baseline to 12 months;

(2) Mean changes in systolic blood pressure (SBP) and diastolic blood pressure (DBP) from baseline to 12 months;

(3) Mean changes in fasting blood glucose (FBG) from baseline to 12 months;

(4) Mean changes in non-HDL cholesterol (non-HDL-C) from baseline to 12 months;

(5) Changes in proportion of overweight and obesity from baseline to 12 months;

(6) Changes in proportion of daily smoking from baseline to 12 months;

(7) Changes in proportion of insufficient physical activity (<3000 MET-min/wk) from baseline to 12 months;

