3.6 Outcome Evaluation

The information of study outcomes (for participants in both intervention and control groups) was collected at baseline and each follow-up visits at 3th month, 6th month, 9th month, and 12th month. All the data collection was conducted using standardized equipment and following uniform operational protocols. These data were collected in three ways: (1) standardized electronic questionnaire interview; (2) physical examination; (3) fingertip blood sample collection.

The primary outcome, 10-year risk of ASCVD, was calculated by the China-PAR prediction model based on age, sex, geographic region (northern/southern China), urbanity, waist circumference, systolic blood pressure (SBP), use of antihypertensive

medication, presence of diabetes, total cholesterol (TC), high-density lipoprotein cholesterol (HDL-C), smoking status, and family history of ASCVD.

Regarding assessment of the metabolic risk factors, to be more specific, blood pressure was measured twice on the right upper arm using a standard sphygmomanometer (Omron HEM-7121, Omron Corporation, Japan) after 5 minutes of rest in the sitting position. Blood glucose and blood lipid were tested by the rapid blood glucose analyser (BeneCheck BK6-20 M Multi-Monitoring System, Suzhou Pu Chun Tang Biotechnology, China) and the fast photochemical lipid analyser (CardioChek PA Analyzer; Polymer Technology Systems, USA), respectively. Body mass index (BMI) was calculated as body weight in kilograms divided by the squared value of height in meters, with obesity was defined as a BMI≥28.0 kg/m².

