Control	(992/2212)	(1295/2197)	(1395/2207)	(1480/2203)	(1556/2200)	P<0.001*
(Mean change	e) Interventior	1: 35.6% (33.5	% to 37.8%),	Control: 25.9%	6 (23.8% to 27.9	%)

Table S5. Exploratory Outcome: Medication adherence

* Medication adherence was defined as taking the full dose of prescribed medications ≥6 days per week among all participants with hypertension, diabetes, or dyslipidaemia. The net group difference was adjusted for clustering effects by villages (as random effect), four minimisation factors, age, sex, education, occupation, annual household income, marriage status, social medical insurance, and baseline level of the outcome.

Fig S4. Exploratory Outcome: MACEs

* The HR and 95%CI of MACEs were estimated by Cox frailty model with adjustment of clustering effects by villages (as random effect), four minimisation factors, age, sex, education, occupation, annual household income, marriage status, and social medical insurance.

	Intervention (n=2246)				Control (n=2	2188)	Net Group Difference	Darahar
	Baseline	12-month	Change (95%CI)	Baseline	12-month	Change (95%CI)	(95%CI)	P value
Primary outcome								
10-year risk of ASCVD, %	18.0 (7.1)	11.7 (5.8)	-6.3 (-6.5 to -6.0)	17.7 (6.8)	13.5 (6.9)	-4.2 (-4.5 to -3.9)	-1.88 (-2.57 to -1.19)	< 0.001
Secondary outcomes								
Lifetime risk of ASCVD, % *	49.9 (15.4)	34.0 (12.7)	-15.9 (-16.4 to -15.3)	49.4 (15.8)	38.4 (14.8)	-11.0 (-11.5 to -10.4)	-4.59 (-6.23 to -2.96)	< 0.001
Systolic blood pressure, mmHg	157.7 (16.2)	134.4 (12.1)	-23.2 (-23.9 to -22.5)	157.0 (16.1)	141.9 (16.1)	-15.0 (-15.8 to -14.3)	-7.70 (-9.38 to -6.02)	< 0.001
Diastolic blood pressure, mmHg	93.4 (11.0)	82.5 (8.0)	-10.9 (-11.3 to -10.4)	92.6 (10.7)	85.8 (9.8)	-6.8 (-7.2 to -6.4)	-3.63 (-4.70 to -2.55)	< 0.001
Fasting blood glucose, mmol/L	7.2 (2.7)	6.3 (1.6)	-0.9 (-1.0 to -0.8)	7.1 (2.5)	6.6 (1.8)	-0.5 (-0.6 to -0.4)	-0.29 (-0.51 to -0.07)	0.009
Non-HDL-C, mmol/L	3.4 (1.2)	3.0 (1.1)	-0.4 (-0.4 to -0.3)	3.4 (1.3)	3.1 (1.1)	-0.3 (-0.4 to -0.3)	-0.06 (-0.19 to 0.08)	0.43
Obesity	869 (38.7%)	784 (34.9%)	-3.8% (-5.0% to -2.6%)	842 (38.5%)	792 (36.2%)	-2.3% (-3.5% to -1.1%)	0.83 (0.65 to 1.05)	0.13
Daily smoking	515 (22.9%)	449 (20.0%)	-2.9% (-4.0% to -1.9%)	473 (21.6%)	462 (21.1%)	-0.5% (-1.5% to 0.4%)	0.61 (0.43 to 0.85)	0.004
Insufficient physical activity	315 (14.0%)	247 (11.0%)	-3.0% (-4.6% to -1.5%)	309 (14.1%)	337 (15.4%)	1.3% (-0.3% to 2.8%)	0.63 (0.42 to 0.94)	0.03
(<3000 MET-min/wk)								

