APPENDIX 4:

ANALYSIS CODE FOR THE STUDY

* Compare Baseline Characteristics; * continuous variables; proc means data=smarter data mean std; var IS age SBP0 DBP0 GLU0 NHDL0 waist0 BMI0 risk0 risk lifetime 0; by group; run; * categorical variables; proc freq data=smarter data; tables male pd education pd labor pd income pd married pd insure smk daily 0 PA 1t3000 0; by group; run; * Evaluation of Research Outcomes; data fu4 data; set smarter data; if risk4^=.; run; proc means data=fu4 data n mean std; var risk0 risk4 risk lifetime 0 risk lifetime 4 SBP0 SBP4 DBP0 DBP4 GLU0 GLU4 NHDL0 NHDL4; by group; run; proc freq data=fu4 data; tables obesity 0 obesity 4 smk daily 0 smk daily 4 PA lt3000 0 PA lt3000 4 LTPA0 LTPA4; by group; run; proc means data=fu4 data n mean clm; var risk4_change risk_lifetime4_change SBP4_change DBP4_change GLU4_change NHDL4 change; by group; run;

* model for continuous variables (eg.10-y ASCVD risk);

proc glimmix data=fu4_data;

class village_id group(ref='2') male education_high_above Last_year_income_lt_10k
occupation_farmer marriage_yes insure_yes vc_risk_grp vc_sbp_grp vc_age_grp
doctor_college_above;
model risk4_change=group risk0 IS_age male education_high_above
Last_year_income_lt_10k occupation_farmer marriage_yes insure_yes vc_risk_grp
vc_sbp_grp vc_age_grp doctor_college_above
/solution dist=normal link=identity ddfm=bw cl ;
random int/subject=village_id type=un;
run;

* model for categorical variables (eg.smk daily);

proc glimmix data=fu4_data;

class village_id group(ref='2') male education_high_above Last_year_income_lt_10k
occupation_farmer marriage_yes insure_yes smk_daily_0 vc_risk_grp vc_sbp_grp
vc_age_grp doctor_college_above;
model smk_daily_4(event="1") =group smk_daily_0 IS_age male education_high_above
Last_year_income_lt_10k occupation_farmer marriage_yes insure_yes vc_risk_grp
vc_sbp_grp vc_age_grp doctor_college_above/solution dist=binary link=logit ddfm=bw cl;
random int/solution subject=village_id type=un;
ods output ParameterEstimates=Coefficients_smk;
run;

data coefficients_smk; set coefficients_smk; if effect~='Intercept' then do; PA_OR=exp(Estimate); PA_OR_L=exp(Estimate-1.96*stderr); PA_OR_U=exp(Estimate+1.96*stderr); PA_OR_95CI=compress(put(PA_OR,4.2))||"("||compress(put(PA_OR_L,4.2))||","||compress(p ut(PA_OR_U,4.2))||")"; end; run; * Subgroup Analysis;

* eg.sex: male/female;

data male; set fu4_data; if male=1; run; data female; set fu4_data; if male=0; run;

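### Secondary outcome (5) is listed as overweight and obesity, but SAP 6.4, the supplied code and Table S6(a) cover obesity only

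*Combined protocol and SAP*

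**What the plan says.** The outcome lists in protocol 3.3.2 and SAP 3.5.2 agree word for word on item (5): "Changes in proportion of overweight and obesity from baseline to 12 months".

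The later sections are narrower:

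- SAP 6.4, on the analysis of secondary outcomes, gives the categorical outcomes as "changes in the proportions of obesity, daily smoking, and insufficient physical activity". Overweight is not mentioned.
- Protocol 5.1 sets one BMI threshold, "with obesity is defined as a BMI≥28.0 kg/m²", and SAP 3.6 repeats it, "with obesity was defined as a BMI≥28.0 kg/m²". Neither section gives a threshold for overweight.
- The outcome code in Appendix 4 tabulates "tables obesity 0 obesity 4 smk daily 0 smk daily 4", with no overweight variable.
- Table S6(a) has one adiposity row, headed Obesity.

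An overweight threshold does exist. Protocol Table 2 (risk factors to be assessed) puts overweight at BMI 24 or above and obesity at BMI 28 or above. Protocol Table 3 also uses BMI 24: for participants below BMI 28 the weight goal is set "with a body weight at BMI 24 as the target weight".

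SAP section 1 asks that departures from the SAP be described and justified in the trial's final report.

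**The concern.** The SAP disagrees with the protocol's outcome list and with its own. The difference is more than loose wording, because Table 2 gives the two terms different thresholds and so they define different groups. An analyst who follows SAP 6.4 and the code as written will leave out part of a listed secondary outcome.

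What is at stake is one secondary outcome. Anyone who starts at BMI 24 to 27.9 is non-obese at baseline. On an obesity-only outcome that person can stay non-obese or move up past 28; a fall below 24 leaves no trace. The reported obesity result therefore says nothing about improvement among overweight participants, although the outcome lists include them.

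**Working it through.** **1. The sections side by side**

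| Place | What it covers | BMI threshold given |
|---|---|---|
| Protocol 3.3.2 (5) | overweight and obesity | none |
| SAP 3.5.2 (5) | overweight and obesity | none |
| Protocol 5.1 | obesity | 28 |
| SAP 3.6 | obesity | 28 |
| SAP 6.4 | obesity | none |
| Appendix 4, outcome code | obesity at baseline and 12 months | derivation not shown |
| Table S6(a) | obesity | none |
| Protocol Table 2 (risk assessment) | both terms, separately | 24 and 28 |

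The two outcome lists include overweight. Every place that defines an outcome variable, analyses it or reports it leaves overweight out.

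**2. Reproducing the reported obesity row (Table S6(a))**

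Proportion = count / group size.

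- Intervention: 869/2246 = 38.7% at baseline and 784/2246 = 34.9% at 12 months, a change of −3.8 points.
- Control: 842/2188 = 38.5% at baseline and 792/2188 = 36.2% at 12 months, a change of −2.3 points.

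These match the table. The reported adjusted odds ratio is 0.83 (95% CI 0.65 to 1.05), P=0.13. The row is internally sound. The question is only which outcome it represents.

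**3. How many participants could be affected**

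Non-obese at baseline = group size − obese.

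- Intervention: 2246 − 869 = 1377, and 1377/2246 = 61.3%.
- Control: 2188 − 842 = 1346, and 1346/2188 = 61.5%.
- Both groups: (1377 + 1346)/(2246 + 2188) = 2723/4434 = 61.4%.

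This is a ceiling. It includes people already below BMI 24, who could not improve on either outcome. The group that matters is BMI 24 to 27.9, and the documents give no count for it at baseline or at 12 months. The overweight-or-obesity proportions, and any odds ratio based on them, cannot be computed from what is supplied.

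**4. Does the weight goal settle which cut is better?**

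Protocol Table 3 sets two kinds of weight goal. Below BMI 28 the target is the weight at BMI 24. At BMI 28 or above it is a loss of 15% of body weight. With height fixed, BMI after a 15% loss is 0.85 × starting BMI.

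- It falls below 24 only if the starting BMI is under 24/0.85 = 28.2.
- It falls below 28 if the starting BMI is under 28/0.85 = 32.9.

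A cut at 24 would therefore miss goal attainment in nearly all participants who start obese. A cut at 28 registers it for starting values from 28 up to about 32.9, but misses improvement in those who start at 24 to 27.9. Neither cut covers both groups, which is a reason to report both.

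**The case against.** Much of the case on the other side stands, and it limits what can be claimed.

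- A reader might infer that the listed outcome was never analysed, or was swapped without disclosure. The documents do not show this. Table S6(a) is a sensitivity table that excludes participants with MACEs, the main results table is not supplied, and SAP section 1 places explanations of departures in a final report that is also not supplied. The model code for categorical outcomes is a worked example for daily smoking, so it does not show every model that was run.
- A reader might infer that SAP 6.4 introduced the narrowing. Protocol 5.1 already defines only obesity, so the inconsistency is within the protocol as well.
- No section states that outcome (5) means BMI 24 or above. One combined category is the natural reading, but the phrase could mean two separate proportions. On that reading obesity is covered and only overweight is missing. Either way, the listed outcome is not covered in full.
- The weight goals might seem to prove the obesity cut wrong. They do not, as step 4 shows.
- A reader might suspect that a favourable cut was chosen. The obesity result is not statistically significant (P=0.13), and nothing in the documents points to selection.

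None of this removes the contradiction between SAP 3.5.2 and 6.4, or gives a reason for leaving overweight out.

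**Conclusion.** Wrong as written, and it should be fixed. The listed outcome and the outcome that SAP 6.4 plans to analyse differ. Overweight is not analysed anywhere in the supplied documents, and they do not explain why.

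The size of the effect on the result is unknown. The affected group is at most about 61% of the participants in Table S6(a) and is probably smaller, since some non-obese participants may already be below BMI 24. The direction of any change in the estimate cannot be stated. The primary outcome, 10-year ASCVD risk, is unaffected, and this is one of seven listed secondary items.

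The conclusion rests on two assumptions: that the obesity variables in the code use the BMI 28 threshold of SAP 3.6, since their derivation is not shown, and that Table 2's cut-offs are the ones meant for outcome (5).

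**What to change.** 1. State the BMI threshold(s) for outcome (5), using the documents' own cut-offs, and say whether it is one combined category or two proportions.
2. Align protocol 3.3.2 and 5.1 with SAP 3.5.2, 3.6 and 6.4.
3. Run the planned generalised linear mixed model, with village as a random effect, on overweight or obesity (BMI 24 or above). Adjust for its baseline status, as the code's daily-smoking example does.
4. Keep obesity (BMI 28 or above) alongside it. If the analysis is to stay restricted to obesity, label that as a change to the listed outcome, with date and reason.

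The cost is one derived variable, one model and one table row, plus the wording changes. No new data are needed: height and weight are part of the physical examination in protocol 5.1, which protocol Table 1 schedules at baseline and at every follow-up visit.

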6.5 Subgroup Analyses

Potential interactions will be explored for the primary outcome by subgroups of age, sex, education, occupation, annual household income, and tertile of baseline 10-year risk of ASCVD, with a statistical significance level of 0.05 (two-sided).

6.6 Opportunities for Adding Unanticipated Assessments

If evidence emerges from other studies to suggest that additional assessments would be of high research value then the statistical analysis plan may be amended to include them (either in all participants or in subsets of sufficient size). Given the controlled nature of the trial, comparisons between the randomized groups of outcomes assessed in this way (i.e., without a baseline assessment) can still provide a reliable unbiased result of the intervention effects.

Reference

None.

		小常识			01 0	45 🎪	17 9	0
assessment GSA114.膝盖疼还能做哪些运动? assessment assessment d健康小常识 assessment dgb: assessment dgb: assessment dgb: assessment dgb: assessment cassessment a	雾霾天? 户外锻炉	可以在			在户外辗	炼吗		
建康小常识 ひのかい ・・・・・・・・・・・・・・・・・・・・・・・・・・・・・	健康	小常识	2023-03	-20 19:55	27 0	47 🍁	21 🗭	1
株定制自己的 (A) (A) (A) (A) (A) (A) (A) (A) (A) (A)	膝盖疼 还能做哪?	553 2			做哪些运	动?		
本部计划 全康小常识 2023-03-16 15:25:49 ● 29 ▲ 12 ● 0 正素里就可以做的 GSA111.在家里就可以做的运动有哪些?	健康	小常识	2023-03	-16 15:27:	45 o	40 🏚	19 🗭	0
· · · · · · · · · · · · · · · · · · ·	怎样定制] 运动计划				己的运动	计划?		
	健康	小常识			49 o	29 🍿	12 🗭	0
	怎样定制 运动计划 健康	alah 小常识	QSA112. 一般人都 2023-03	怎样制定自 ¥ 16 15:25: 在家里就可	己的运动 49 0	计划? 29 曲	12 🗭	
	Home Menu	A A O CHARA						N
Internet in the second se	系统首页	5 健康	知识	■ 健康档案	信息纸	5it	我的	

13

*

.

收藏 评论

* 🖽 🤶 🛍 🛍 🚯

...

☑ 张一

🖸 张二

🖸 张三

 \odot

V

☑ 唐一

☑ 唐二

Х

Months	Number of short videos	Number of short videos	Number of short videos	Proportion of short videos
months	successfully forwarded	unwatched	viewed	viewed
3	44693	28811	15882	35.5%
4	50446	26526	23920	47.4%
5	47989	25244	22745	47.4%
6	50229	20062	30167	60.1%
7	49521	15356	34165	69.0%
8	49750	11070	38680	77.7%
9	49116	6933	42183	85.9%
10	53404	7038	46366	86.8%
11	45404	7804	37600	82.8%
12	49834	8792	41042	82.4%

 Table S1. Adherence statistics for targeted health education short videos

Table S2. Satisfaction statistics for targeted health education short videos

	Numbers of	Question: Do you think the short videos	Question: Do you think the short	Question: Would you like to continue to
Follow-up visit		are relevant to your health conditions?	videos are useful?	receive short videos after the study ends?
	respondents	Answer: YES	Answer: YES	Answer: YES
3rd month	2268	98.9% (2244)	98.6% (2236)	N/A
6th month	2265	98.9% (2239)	98.9% (2240)	N/A
9th month	2268	98.9% (2242)	98.6% (2237)	N/A
12th month	2284	N/A	N/A	87.6% (2000)
Total		98.9% (6725/6801)	98.7% (6713/6801)	87.6% (2000/2284)

Mantha		Wearing≥3 days p	er week	Wearing ≥5 days per week		
Months	Total number (person-week) –	Number (person-week)	Proportion	Number (person-week)	Proportion	
3	8824	5064	57.4%	4314	48.9%	
4	8824	6067	68.8%	5455	61.8%	
5	8824	6063	68.7%	5482	62.1%	
6	8824	6680	75.7%	5929	67.2%	
7	11030	8794	79.7%	7860	71.3%	
8	8824	7614	86.3%	6814	77.2%	
9	11030	10040	91.0%	9168	83.1%	
10	8824	8070	91.5%	7474	84.7%	
11	8824	7515	85.2%	6760	76.6%	
12	11030	9614	87.2%	8725	79.1%	

Table S3. Adherence statistics for health monitoring using smart bands

(a) Smart band wearing statistics

(b) Daily step target achieving statistics

Mantha	Initial Total number (person-week) 3 8824 4 8824 5 8824 6 8824 7 11030 8 8824	Target achieved ≥3 day	vs per week	Target achieved ≥5 days per week		
wiontins	Total number (person-week) –	Number (person-week)	Proportion	Number (person-week)	Proportion	
3	8824	3152	35.7%	1814	20.6%	
4	8824	3383	38.3%	2013	22.8%	
5	8824	3145	35.6%	1839	20.8%	
6	8824	3755	42.6%	2240	25.4%	
7	11030	5817	52.7%	3684	33.4%	
8	8824	5266	59.7%	3661	41.5%	
9	11030	6525	59.2%	4492	40.7%	
10	8824	5403	61.2%	3773	42.8%	
11	8824	5036	57.1%	3416	38.7%	
12	11030	7006	63.5%	4997	45.3%	

6	Awareness			Treatment		
Group	at baseline	Baseline	3rd month	6th month	9th month	12th month
Hypertension (n=4390)						
Intervention (n=2234)	88.3% (1973/2234)	41.4% (924/2234)	64.5% (1423/2207)	68.8% (1517/2205)	71.5% (1579/2208)	74.8% (1663/2222)
Control (n=2156)	89.1% (1921/2156)	41.6% (896/2156)	55.0% (1178/2142)	60.5% (1302/2151)	63.2% (1357/2147)	65.4% (1403/2144)
Diabetes (n=2262)						
Intervention (n=1131)	66.1% (748/1131)	27.6% (312/1131)	39.8% (446/1120)	44.7% (500/1119)	46.0% (516/1121)	47.3% (532/1125)
Control (n=1131)	63.8% (721/1131)	27.6% (312/1131)	34.5% (387/1123)	37.7% (425/1128)	39.4% (444/1126)	41.0% (461/1125)
Dyslipidaemia (n=2479)						
Intervention (n=1207)	N/A	12.7% (153/1207)	18.8% (225/1195)	22.0% (262/1192)	25.0% (298/1192)	28.7% (345/1201)
Control (n=1272)	N/A	15.9% (202/1272)	18.5% (234/1265)	19.3% (245/1270)	21.1% (268/1268)	20.7% (262/1266)

Table S4. Awareness and treatment of hypertension, diabetes, and dyslipidaemia

[figure not shown]
* Based on the baseline data, the three conditions were defined as follows: (1) Hypertension was defined as an average SBP \geq 140 mmHg, or an average DBP \geq 90 mmHg, or a self-reported history of hypertension, or in the use of antihypertensive medications; (2) Diabetes was defined as a FBG \geq 7 mmol/L, or a self-reported history of diabetes, or in the use of antidiabetic medications; (3) Dyslipidaemia was defined as TC \geq 6.2 mmol/L, or LDL-C \geq 4.1 mmol/L, or TG \geq 2.3 mmol/L, or HDL-C<1.0 mmol/L, or in the use of lipid-lowering medications.

Group	Baseline	3rd months	6th months	9th months	12 months	Net Group Difference (OR, 95%CI)
Intervention	45.1%	64.7%	71.2%	76.2%	80.7%	
Intervention	(1031/2287)	(1462/2258)	(1606/2256)	(1721/2259)	(1835/2275)	1.99
Control	44.8%	58.9%	63.2%	67.2%	70.7%	(1.46 to 2.71)
Control	(992/2212)	(1295/2197)	(1395/2207)	(1480/2203)	(1556/2200)	P<0.001*
(Mean change	e) Interventior	1: 35.6% (33.5	% to 37.8%),	Control: 25.9%	6 (23.8% to 27.9	%)

Table S5. Exploratory Outcome: Medication adherence

* Medication adherence was defined as taking the full dose of prescribed medications ≥6 days per week among all participants with hypertension, diabetes, or dyslipidaemia. The net group difference was adjusted for clustering effects by villages (as random effect), four minimisation factors, age, sex, education, occupation, annual household income, marriage status, social medical insurance, and baseline level of the outcome.

Fig S4. Exploratory Outcome: MACEs

* The HR and 95%CI of MACEs were estimated by Cox frailty model with adjustment of clustering effects by villages (as random effect), four minimisation factors, age, sex, education, occupation, annual household income, marriage status, and social medical insurance.

	Intervention (n=2246)				Control (n=2	2188)	Net Group Difference	Darahar
	Baseline	12-month	Change (95%CI)	Baseline	12-month	Change (95%CI)	(95%CI)	P value
Primary outcome								
10-year risk of ASCVD, %	18.0 (7.1)	11.7 (5.8)	-6.3 (-6.5 to -6.0)	17.7 (6.8)	13.5 (6.9)	-4.2 (-4.5 to -3.9)	-1.88 (-2.57 to -1.19)	< 0.001
Secondary outcomes								
Lifetime risk of ASCVD, % *	49.9 (15.4)	34.0 (12.7)	-15.9 (-16.4 to -15.3)	49.4 (15.8)	38.4 (14.8)	-11.0 (-11.5 to -10.4)	-4.59 (-6.23 to -2.96)	< 0.001
Systolic blood pressure, mmHg	157.7 (16.2)	134.4 (12.1)	-23.2 (-23.9 to -22.5)	157.0 (16.1)	141.9 (16.1)	-15.0 (-15.8 to -14.3)	-7.70 (-9.38 to -6.02)	< 0.001
Diastolic blood pressure, mmHg	93.4 (11.0)	82.5 (8.0)	-10.9 (-11.3 to -10.4)	92.6 (10.7)	85.8 (9.8)	-6.8 (-7.2 to -6.4)	-3.63 (-4.70 to -2.55)	< 0.001
Fasting blood glucose, mmol/L	7.2 (2.7)	6.3 (1.6)	-0.9 (-1.0 to -0.8)	7.1 (2.5)	6.6 (1.8)	-0.5 (-0.6 to -0.4)	-0.29 (-0.51 to -0.07)	0.009
Non-HDL-C, mmol/L	3.4 (1.2)	3.0 (1.1)	-0.4 (-0.4 to -0.3)	3.4 (1.3)	3.1 (1.1)	-0.3 (-0.4 to -0.3)	-0.06 (-0.19 to 0.08)	0.43
Obesity	869 (38.7%)	784 (34.9%)	-3.8% (-5.0% to -2.6%)	842 (38.5%)	792 (36.2%)	-2.3% (-3.5% to -1.1%)	0.83 (0.65 to 1.05)	0.13
Daily smoking	515 (22.9%)	449 (20.0%)	-2.9% (-4.0% to -1.9%)	473 (21.6%)	462 (21.1%)	-0.5% (-1.5% to 0.4%)	0.61 (0.43 to 0.85)	0.004
Insufficient physical activity	315 (14.0%)	247 (11.0%)	-3.0% (-4.6% to -1.5%)	309 (14.1%)	337 (15.4%)	1.3% (-0.3% to 2.8%)	0.63 (0.42 to 0.94)	0.03
(<3000 MET-min/wk)								
Insufficient leisure-time activity (<150/75 min/wk)	1541 (68.6%)	1040 (46.3%)	-22.3% (-24.7% to -19.9%)	1420 (64.9%)	1372 (62.7%)	-2.2% (-4.5% to 0.1%)	0.38 (0.24 to 0.59)	< 0.001

* Data were mean (SD), n (%), mean (95%CI) or OR (95%CI) unless otherwise stated.

All net group difference was adjusted for clustering effects by villages (as random effect), four minimisation factors, age, sex, education, occupation, annual household income, marriage status, social medical insurance, and baseline level of the outcome.

	Interv	ention (n=2246)	Co	ntrol (n=2188)	Net Group Difference	D l	D :
Subgroup	Number	Changes (95%CI)	Number	Changes (95%CI)	(95%CI)	P value	P-inter
Age, year							0.73
<60	1352	-7.0 (-7.3 to -6.6)	1301	-5.2 (-5.6 to -4.9)	-1.86 (-2.57 to -1.16)	< 0.001	
≥60	894	-5.2 (-5.6 to -4.8)	887	-2.7 (-3.1 to -2.3)	-1.82 (-2.63 to -1.01)	< 0.001	
Sex							0.03
Male	1130	-7.2 (-7.6 to -6.7)	1062	-4.6 (-5.0 to -4.2)	-2.20 (-3.05 to -1.36)	< 0.001	
Female	1116	-5.4 (-5.7 to -5.1)	1126	-3.8 (-4.1 to -3.5)	-1.55 (-2.20 to -0.90)	< 0.001	
Education							0.74
Below high school	1755	-6.0 (-6.3 to -5.7)	1749	-4.1 (-4.4 to -3.9)	-1.83 (-2.54 to -1.12)	< 0.001	
High school and above	491	-7.3 (-7.9 to -6.7)	439	-4.4 (-5.0 to -3.7)	-2.11 (-3.03 to -1.20)	< 0.001	
Occupation							0.03
Farmer	1535	-6.1 (-6.4 to -5.8)	1465	-4.4 (-4.7 to -4.0)	-1.63 (-2.41 to -0.85)	< 0.001	
Non-farmer	711	-6.6 (-7.1 to -6.1)	723	-3.8 (-4.3 to -3.4)	-2.60 (-3.37 to -1.83)	< 0.001	
Annual household income, yuan							0.02
<10 000	358	-5.1 (-5.8 to -4.5)	347	-2.4 (-3.1 to -1.8)	-2.76 (-3.90 to -1.63)	< 0.001	
≥10 000	1888	-6.5 (-6.8 to -6.2)	1841	-4.5 (-4.8 to -4.2)	-1.72 (-2.40 to -1.03)	< 0.001	
10-year risk of ASCVD, %							< 0.001
<16	1128	-3.5 (-3.7 to -3.3)	1128	-2.3 (-2.6 to -2.0)	-1.14 (-1.76 to -0.52)	< 0.001	
≥16	1118	-9.0 (-9.5 to -8.6)	1060	-6.2 (-6.6 to -5.8)	-2.57 (-3.42 to -1.72)	< 0.001	

 Table S6 (b). Subgroup results of the primary outcome (sensitivity analysis: excluding participants with MACEs)

